### 3.2.19 Completer cohorts

A completer cohort will be defined as the subset of subjects in the Full Analysis Set (FAS) that were enrolled and treated with LCM for a specified duration of time. For example, a 6-month completer cohort consists of subjects enrolled and treated with LCM for at least 6 months where a month is defined as 28 days.

Subjects will be classified as belonging to one of the following completer cohorts for the purpose of subgroup analyses:

- 6 months
- 12 months
- 18 months
- 24 months

### **3.2.20 Number and percentage of seizure-free days**

The number of seizure-free days will be the total number of days within an interval for which daily diary data was available and no seizures were reported. The percentage of seizure-free days will be computed as 100 times the number of seizure-free days in the interval divided by the number of days in the interval for which daily diary data was available. Days without the corresponding daily diary data will not be used in these computations (ie, days where “not done” is marked on the Seizure Frequency eCRF module). The change in percentage of seizure-free days will be calculated relative to Baseline (using the Baseline definition in [Section 3.3](#)).

### **3.2.21 Seizure time intervals**

Subjects will be classified as belonging to one of the following time intervals for the purpose of seizure efficacy analyses:

- $\leq 3$  months
- $> 3$  to  $\leq 6$  months
- $> 6$  to  $\leq 12$  months
- $> 12$  to  $\leq 18$  months
- $> 18$  to  $\leq 24$  months
- $\geq 24$  months

### **3.2.22 Pediatric Quality of Life Inventory (PedsQL)**

The PedsQL is a validated instrument that consists of generic core scales suitable for use with pediatric populations, including those with acute or chronic health conditions. Self-report is measured for pediatric subjects  $\geq 5$  years to  $\leq 18$  years of age, and parent proxy report of child health-related quality of life (HRQoL) is measured for pediatric subjects  $\geq 1$  month to  $\leq 4$  years of age. The PedsQL Measurement Model consists of developmentally appropriate forms for pediatric study subjects  $\geq 1$  month to  $\leq 12$  months,  $\geq 13$  months to  $\leq 24$  months,  $> 2$  years to  $\leq 4$  years,  $\geq 5$  years to  $\leq 7$  years,  $\geq 8$  years to  $\leq 12$  years, and  $\geq 13$  years to  $\leq 18$  years of age. For each subject, the same version that is used at Baseline should be used for 12 months and thereafter the age appropriate age versions should be used.

For versions intended for subjects  $\leq 24$  months of age, PedsQL infant scale scores will be calculated for each of the following 5 PedsQL scales:

- Physical Functioning

- Physical Symptoms
- Emotional Functioning
- Social Functioning
- Cognitive Functioning

For versions intended for subjects >2 years of age, PedsQL generic core scale scores will be calculated for each of the following 4 PedsQL scales:

- Physical Functioning
- Emotional Functioning
- Social Functioning
- School Functioning

For versions intended for subjects >8 years of age, Physical Functioning refers to questions “About my health and activities”; Emotional Functioning refers to questions “About my feelings”; Social Functioning refers to questions “How I get along with others”; School Functioning refers to questions “About school”.

The PedsQL assessment is retrospective to the prior one month, and individual items are scored using a 5-point Likert scale (0 to 4 representing responses of: never, almost never, sometimes, often, or almost always). These scores of 0 to 4 will be transformed by the following formula in order to generate scores of 0, 25, 50, 75, and 100 where a higher value represents a better health-related quality of life (HRQoL):

$$\text{Item transformed score} = 100 - (\text{item raw score} \times 25)$$

Each PedsQL scale or dimension score is then calculated as the mean of the transformed item scores from items of the considered dimension. In the case of item-level missing data, these will be replaced by the average of non-missing item scores from the considered dimension, if at least 50% of the items from that dimension are non-missing.

The above algorithm will also be used to calculate the PedsQL total score (all items), the psychosocial health summary score (a combination of the emotional, social and cognitive functioning items), and the physical health summary score (a combination of the physical functioning and physical symptoms items) for each subject  $\leq 24$  months of age. Also, the PedsQL total score (all items), the psychosocial health summary score (a combination of the emotional, social and school functioning items) and the physical health summary score (the physical functioning items) will be calculated for each subject >2 years of age. These summary scores will be missing if any of the scale scores contributing to their calculation is missing.

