9.3 PedsQL

The PedsQL is a validated instrument that consists of generic core scales suitable for use with pediatric populations, including those with acute or chronic health conditions (Varni et al, 2001). The PedsQL will be administered according to the tabular schedules of study procedures (Section 5.2). The PedsQL will only be administered in countries where a validated translated version is available.

The PedsQL measurement model consists of developmentally appropriate forms for pediatric subjects 1 month to 12 months, 13 months to 24 months, 2 years to 4 years, 5 years to 7 years, 8 years to 12 years, and 13 years to 18 years of age. Self-report is measured for pediatric subjects ≥ 5 years to ≤ 18 years of age, and parent proxy report of child health-related quality of life (HRQoL) is measured for pediatric subjects ≤ 4 years of age. The PedsQL appropriate for each subject's age should be completed, with the following exception: If a subject ages up to the next form of the PedsQL within 1 year after the Baseline assessment of the primary study, the form that was used at the Baseline assessment should be completed for 1 year after the Baseline assessment, and subsequently the form consistent with his/her age at the time of assessment should be completed.

The multidimensional PedsQL generic core scales encompass the essential core domains for pediatric HRQoL measurement: Physical Functioning, Emotional Functioning, Social Functioning, and School Functioning. The PedsQL assessment is retrospective to the prior 4 weeks, and individual items are scored using a 5-point Likert scale (never, almost never, sometimes, often, or always). A total health summary score ranging between 0 and 100 is calculated from the sum of the raw scores, with higher scores indicating higher HRQoL.

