#### **9.2.3.1 Pediatric Quality of Life Inventory Ages for $\leq 24$ Months**

The multidimensional PedsQL  $\leq 24$  months generic core scales encompass the following core domains for pediatric HRQoL measurement: Physical Functioning, Physical Symptoms, Emotional Functioning, Social Functioning, and Cognitive Functioning.

Calculated values and changes from Baseline for the total scale score (all items), the psychosocial health summary score, the physical health summary score and each of the 5 scale scores will be summarized for each visit and for Last Visit. This will be repeated by enrollment group. All changes from Baseline will only be calculated for visits when the subject uses the same form of the questionnaire as administered at baseline.

All PedsQL  $\leq 24$  months data will be listed.

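### PedsQL psychosocial and physical summary scores are assigned by the child's age, while the scale scores follow the form completed, so the two can disagree for children who start on an infant form

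*SAP*

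**What the plan says.** SAP Section 3.2.22 scores the PedsQL in two steps.

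- **Scale scores follow the form.** The infant versions (1–12 and 13–24 months) give five scales: Physical Functioning, Physical Symptoms, Emotional, Social and Cognitive Functioning. The older versions give four: Physical, Emotional, Social and School Functioning. The wording is version-based: "For versions intended for subjects >2 years of age, PedsQL generic core scale scores will be calculated" for those four.
- **Summary scores follow the child.** At or below 24 months, psychosocial health combines emotional, social and cognitive items, and physical health combines physical functioning and physical symptoms. Above 2 years, school items replace cognitive items in the psychosocial score, and "the physical health summary score (the physical functioning items) will be calculated for each subject >2 years of age". The total is all items in both branches. The date at which age is taken is not stated.
- **Missing rule.** "These summary scores will be missing if any of the scale scores contributing to their calculation is missing".

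The form is held fixed for a year. The SAP says "the same version that is used at Baseline should be used for 12 months and thereafter the age appropriate age versions should be used". Protocol Section 9.3 says "the form that was used at the Baseline assessment should be completed for 1 year after the Baseline assessment", with Baseline being that of the primary study.

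SAP Section 9.2.3 refers to Section 3.2.22 for scoring. Section 9.2.3.1 reports the summary scores next to the infant scales ("each of the 5 scale scores will be summarized for each visit and for Last Visit") and restricts change from Baseline to visits on the Baseline form. Section 9.2.3.2 lists four scales and applies the same restriction to children under 5 years at Baseline. Protocol Tables 5-1 and 5-2 schedule the PedsQL at Weeks 0, 20, 52, 72 and 96 and at early termination. The Week 0 assessment is not repeated if it was done at the final Maintenance Visit of the primary study.

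**The concern.** A rule keyed to the form and a rule keyed to age give the same result only while age and form agree, and the 12-month retention rule makes them part. For a child who passes 24 months on the 13–24-month form, or who later moves to an older form, Section 3.2.22 can call for a scale that the completed form does not contain.

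A missing summary score is at least visible. The physical summary is worse, because the older-child formula can be computed on an infant form. It gives a plausible number, built from fewer items than the Baseline value against which it is compared. Week 20 is the main post-entry visit at which infant-form change from Baseline can be computed, so that is where the mismatch would show.

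**Working it through.** The plan gives no figure to reproduce on this point. The check is to find when age and form can disagree, then apply the stated rule under each reading of age.

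**1. Who can be past 24 months on an infant form.** With the form kept for 12 months, the months of mismatch are max(0, *a* + 12 − 24), where *a* is age in months at the primary-study Baseline.

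| *a* (months) | 12 or less | 13 | 15 | 18 | 21 | 24 |
|---|---|---|---|---|---|---|
| Months past 24 on the infant form | 0 | 1 | 3 | 6 | 9 | 12 |

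Only children on the 13–24-month form are exposed in this way.

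**2. Which visits fall in the retention year.** The gap *G* from primary Baseline to Visit 1 of this study is not in the documents. A visit at week *w* is inside the year if *G* + *w* ≤ 365.25/7 = 52.18 weeks.

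- Assumed *G* of 8 to 32 weeks: Weeks 0 and 20 are inside (at the upper end, 32 + 20 = 52).
- Assumed *G* of 36 to 40 weeks: only Week 0 is inside (36 + 20 = 56).
- Week 52 would need *G* ≤ 0.18 weeks, so Weeks 52, 72 and 96 come after the year.

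At Week 20 a child is past 24 months if *a* > 24 − (*G* + 20) × 7/30.4375. The threshold is 17.6 months for *G* = 8, 15.7 for *G* = 16, 13.9 for *G* = 24 and 12.0 for *G* = 32.

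**3. Age read as age at assessment.** Take a child past 24 months who is still on the 13–24-month form.

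- Psychosocial = emotional + social + school. The form has no School scale, so the score is missing under the SAP's own rule.
- Physical = Physical Functioning only, whereas Baseline used Physical Functioning plus Physical Symptoms. As an illustration, suppose the two scales score 50 and 25 at both visits and carry equal weight. Baseline is (50 + 25)/2 = 37.5 and the later value is 50, so a change of +12.5 appears although nothing changed.
- Total = all items of the completed form, and can be computed unless School is counted as a contributing scale.

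**4. Age read as age at Baseline.** Step 3 does not arise. After the move to a form for children over 2 years, however, the infant formulas still apply.

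- Psychosocial needs Cognitive Functioning and physical needs Physical Symptoms. The older form has neither, so both observed summaries are missing.
- Change from Baseline is not at stake, because it is not calculated across these forms for children under 5 years at Baseline.
- This reading can also reach children who began on the 1–12-month form. Week 96 is 96 × 7/30.4375 = 22.1 months after Visit 1, so a child aged 1 month at Baseline is past 24 months there if the gap exceeds 24 − 1 − 22.1 = 0.9 months.

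**5. Summary scores keyed to the form.** Every infant-form assessment uses the cognitive and physical-symptom items it has, and every older-form assessment uses the school items it has. No mismatch remains at any age.

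**The case against.** The strongest reply is that the intent is plain. Sections 9.2.3.1 and 9.2.3.2 pair the summary scores with five and four scales respectively, so their age labels name families of forms, and a programmer would probably score by form. In addition, the SAP cites Section 3.2.24 where it wants age at assessment (Sections 8.3, 8.4.1 and 8.4.2), and Section 3.2.22 does not. The explicit PedsQL age rules, in Sections 3.1 and 9.2.3.2, use age at Baseline. On that reading the Week 20 problem disappears. Finally, the PedsQL is an 'other' efficacy variable in a descriptive study, and all PedsQL data are to be listed, so correct scores could be rebuilt.

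Much of this stands. The intent is form-based and the consequence is small. But Section 3.2.22 is the operative scoring rule, and its summary-score sentences do not say what the layout implies. The Baseline-age reading moves the gap to later visits without closing it.

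**Conclusion.** The inconsistency is real and minor. Section 3.2.22 as worded fails on either reading of age: at assessment, for children past 24 months still on the 13–24-month form; at Baseline, for children who have moved from an infant form to one for children over 2 years. It touches two summary scores. The conflict follows from the text alone; which visits are affected depends on the unstated gap between primary Baseline and Visit 1.

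A reader might infer more than the documents support:

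- **That children receive a score from a School scale their form lacks.** They do not: the missing rule leaves the psychosocial score blank.
- **That the total score is lost.** It is defined as all items, with no School-specific formula, so this holds only if an absent scale counts as contributing.
- **That the remaining infant-form children get a distorted physical score.** On the age-at-assessment reading, the missing psychosocial score and the altered physical score fall on the same children; those at or below 24 months are scored correctly.
- **That most children on the 13–24-month form are affected at Week 20.** Week 20 is 20 × 7/30.44 = 4.6 months. With ages uniform over 12 months and a gap of 1.5 to 5 months, the share would be (4.6 + 1.5)/12 = 51% to (4.6 + 5)/12 = 80%. Neither the age distribution nor the gap is given, and the figure presumes age at assessment. The number of infants is also unknown, and the PedsQL is used only where a validated translation exists. The number affected cannot be derived.

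**What to change.** In SAP Section 3.2.22, where the summary scores are defined, replace the two references to the subject's age by references to the form: *for each assessment completed on an infant version (1–12 or 13–24 months)* and *for each assessment completed on a version for children older than 2 years*. State in Sections 9.2.3.1 and 9.2.3.2 that assessments are assigned to one or the other by the form used.

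This brings the summary scores into line with the version-based rule that the section already applies to the scale scores. The cost is two phrases and one clarifying sentence, with no new data and no change to the visit schedule.

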### 3.2.23 Hospital stay duration

The duration of each hospital stay will be calculated as the discharge date minus the admission date (Hospitalization/Emergency Room [ER] Visit Date on the eCRF module) plus 1 day for hospital stays with a discharge date.

### 3.2.24 Age at time of visit/assessment

If date of birth is a complete date then age at the time of visit/assessment will be calculated as:

$$(\text{Date of visit} - \text{date of birth})/365.25$$

If date of birth is a partial date then age at the time of visit/assessment will be calculated as:

$$(\text{Enrollment age in years}) + [(\text{date of visit} - \text{informed consent date})/365.25]$$

This is converted to months by multiplying by 12 if required.

### 3.3 Definition of Baseline values

In general, Baseline will be defined as the last non-missing value collected prior to the first dose of LCM in the previous pediatric studies for efficacy and safety variables, unless otherwise noted for a specific type of data.

The Baseline value for seizure counts (only applicable for subjects from SP0969) will be taken from the subject diary completed during the 8-week Baseline Period before receiving LCM in study SP0969.

### 3.4 Protocol deviations

Important protocol deviations are deviations from the protocol which could potentially have a meaningful impact on either the primary or secondary outcomes for an individual subject. The criteria for identifying important protocol deviations and the classification of important protocol deviations will be defined separately in an important protocol deviations document. To the extent feasible, rules for identifying protocol deviations will be pre-defined without review of the data and without consideration of the frequency of occurrence of such deviations. Whenever possible, criteria for identifying important protocol deviations will be implemented algorithmically to ensure consistency in the classification of important protocol deviations across all subjects.

In general, protocol deviations will be considered according to the following general categories:

- Inclusion criteria
- Exclusion criteria
- Withdrawal criteria
- Prohibited concomitant medications
- LCM dosing regimen
- Procedural non-compliance

Important protocol deviations will be reviewed as part of the Data Evaluation Meetings (DEMs) and Data Cleaning meetings prior to database lock. A list of subjects with important protocol deviations will be agreed upon during the DEMs and will be documented in the DEM minutes.

In addition, protocol deviations related to the impact of the global pandemic of coronavirus disease 2019 (COVID-19) will be documented.

### 3.5 Analysis sets

#### 3.5.1 Safety Set

The Safety Set (SS) will consist of all enrolled subjects who took at least 1 dose of LCM in this long-term study. All safety analyses will be performed on the SS.

### **3.5.2 Full Analysis Set**

The Full Analysis Set (FAS) will be used for the analysis of seizure data and will consist of all subjects in the SS, who have at least 1 completed post-Baseline seizure diary. Subjects whose efficacy data could not be source verified will be excluded from the FAS.

### **3.6 Treatment assignment and treatment groups**

This is an open-label study; subjects will not be randomized.

Where specified within this SAP, data will be summarized by age group (defined in Section 3.1).

### **3.7 Center pooling strategy**

No pooling of centers is planned for this study.

### **3.8 Coding dictionaries**

Medical history and AEs will be coded using the Medical Dictionary for Regulatory Activities (MedDRA® v16.1). Medications will be coded using the World Health Organization Drug Dictionary (WHODD SEP/2013). Medical procedures will not be coded.

### **3.9 Changes to protocol-defined analyses**

#### **3.9.1 Examination of subgroups**

A number of subgroups which were not protocol-defined have been included in Section 3.2.

#### **3.9.2 Planned safety analyses**

For planned safety analyses, the protocol states that:

Summary tables will be presented over the Treatment Period by 3-month periods and by categories of total duration of exposure.

However, only select AE tables will be presented by 3-month time intervals; incidence of all TEAEs with onset during the Treatment Period, incidence of all serious TEAEs with onset during the Treatment Period, incidence of drug-related TEAEs, incidence of TEAEs by maximum intensity, incidence of all TEAEs leading to discontinuation with onset during the Treatment Period, and incidence of all other significant TEAEs with onset during the Treatment Period.

## **4 STATISTICAL/ANALYTICAL ISSUES**

### **4.1 Adjustments for covariates**

No statistical testing is planned; therefore, this section is not applicable for this study.

### **4.2 Handling of dropouts or missing data**

#### **4.2.1 Missing data**

No imputation of missing values for analysis parameters is planned unless otherwise noted. Imputations for missing or partial values for dates for AEs and concomitant medications will be applied to determine if an event is to be considered treatment-emergent or concomitant. Across safety and efficacy analysis, only reported data will be used in each analysis time interval.

With respect to AEs, events with missing intensity will be assumed to be severe. Events with missing relationship to LCM per the investigator will be assumed to be related. Incomplete or missing dates for events will be handled as described in [Section 4.2.2](#).

#### 4.2.2 Incomplete dates for adverse events and concomitant medications

For analyses of AEs and concomitant medication usage, a complete date must be established in order to correctly identify the AE or medication as occurring during treatment or not. For purposes of imputing missing components of partially-reported start and stop dates for AEs and for medication use, the algorithms listed below will be followed. Start and stop dates of AEs or concomitant medication will be displayed as reported in the subject data listings (ie, no imputed values will be displayed in data listings).

- Missing start day, but month and year present:

If the start of LCM occurred in the same month and year as the occurrence of the AE/concomitant medication, the start day of the event/concomitant medication will be assigned to the day of first intake of LCM. Otherwise the start day will be set to the 1st day of the month.

- Missing start day and month, but year present:

If the start of LCM occurred in the same year as the occurrence of the AE/concomitant medication, the start day and month will be assigned to the date of first intake of LCM. Otherwise the start day and month will be set to January 1st.

- Missing end day, but month and year present:

The end day will be set to the last day of the month.

- Missing end day and month, but year present:

The end day and month will be set to the maximum of the date of study termination or the date equivalent to 30 days after last intake of LCM

However, if the study termination year and year for the date which is 30 days after last intake of LCM are greater than the event/concomitant medication year, the day and month are to be set to December 31st.

#### 4.2.3 Definition of concomitant medication in case of missing dates

With respect to definition of medication as concomitant, the following rule will be applied in case of completely missing stop and/or start date information:

Medications with a missing start date whose stop date is either unknown or after the date of the first dose of LCM will be considered as concomitant medication. Medications with missing start date whose stop date is prior to first intake of LCM will not be considered concomitant.

In subject data listings, dates will be displayed as reported.

